8.3 MULTIPLE COMPARISONS AND MULTIPLICITY

No multiple comparison adjustments are planned for analysis of APD811-007.

8.4 ASSESSMENT WINDOWS

For efficacy and safety assessments, baseline is defined as the last measurement prior to the first dose of ralinepag in the APD811-007 study.

Summary analyses will usually be based on the scheduled (nominal) visits with no visit windows applied. If appropriate, hemodynamic parameters will only be summarized by the Baseline and post-Baseline Visits of APD811-007.

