2 STUDY OBJECTIVES

2.1 PRIMARY OBJECTIVE

To evaluate the long-term safety and tolerability of ralinepag in subjects with WHO Group 1 PAH who have completed Study APD811-003.

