4 STUDY POPULATION SELECTION

4.1 STUDY POPULATION

The study population will include subjects with WHO Group 1 PAH who have completed Study APD811-003 or who were assigned to placebo and discontinued for clinical worsening and who are deemed appropriate candidates for participation in this long-term extension study.

All women, regardless of childbearing potential, must have a negative serum human chorionic gonadotropin (hCG) pregnancy test at each visit during the Treatment Period and at Week 5 of the Dose Titration Period, if applicable. Males and females of childbearing potential must use adequate means of contraception and must agree not to participate in a conception process (ie, active attempt to become pregnant or impregnation, sperm donation, in vitro fertilization) during the study and for 30 days after the last dose of study drug. Eligible subjects must meet all entry criteria prior to being randomized to receive study drug as outlined below. Any deviations from these criteria must be approved by the Sponsor prior to the subject being enrolled.

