4.2 INCLUSION CRITERIA

Each subject must meet the following criteria to be enrolled into the study:

- Evidence of a personally signed and dated informed consent document
- Is willing and able to comply with scheduled visits, treatment plan, laboratory tests, and other study procedures and is deemed an appropriate candidate for participation in this long-term extension study
- Eligible female subjects will be:
 - Nonpregnant, evidenced by a negative serum hCG pregnancy test at Baseline
 - Nonlactating
 - Surgically sterile or postmenopausal, or agree to continue to use an accepted method of birth control for at least 3 months prior to first dose, during, and for at least 30 days after last study drug administration
 - Acceptable methods of birth control are: hormonal contraceptives, double barrier method, intrauterine device, surgical sterility for at least **6 months** prior to Screening for tubal ligation performed laparoscopically, surgical sterility for at least **6 months** prior to Screening by hysterectomy and/or bilateral oophorectomy, and/or postmenopausal status (defined as at least **2 years** without menses). Intended abstinence is not considered an acceptable method

of birth control for this study; subjects must agree to use an acceptable method of birth control should they become sexually active during the study or within **30 days** after the last dose of study drug.

- Eligible male subjects will either be:
 - Surgically sterile (ie, vasectomy) for at least 3 months prior to Screening
 - Agree to use a condom with spermicide when sexually active with a female partner who is not using an acceptable method of birth control during the study and for 30 days after last study drug administration
- Eligible male and female subjects must agree not to participate in a conception process (ie, active attempt to become pregnant or impregnation, sperm donation, in vitro fertilization) during the study and for 30 days after the last dose of study drug
- Fulfilled all eligibility criteria for Study APD811-003 and completed the study as planned
 - Subjects who were assigned to placebo in Study APD811-003 and experienced clinical worsening in that study may enroll in Study APD811-007 after he/she has completed all end of study procedures per protocol, including RHC, and have had their individual Study APD811-003 data locked.

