2 STUDY OBJECTIVES AND ENDPOINTS

2.1 OBJECTIVES

The study objectives are to:

- Evaluate the long-term safety and tolerability of ralinepag in subjects with World Health Organization (WHO) Group 1 pulmonary arterial hypertension (PAH) who have completed Study APD811-003.
- Evaluate the effect of ralinepag in subjects with WHO Group 1 PAH who completed Study APD811-003, as determined by the incidence of clinical worsening.
- Evaluate changes from baseline in 6-Minute Walk Distance (6MWD), WHO/New York Heart Association Functional Class (FC), and hemodynamics.

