9.3.3 PAH History

The listing of PAH history will be organized by treatment group in the parent study, and will include the subject number, the date of initial PAH diagnosis, number of years since PAH diagnosis, PAH classification, WHO FC at Baseline, 6MWD at Baseline, PVR at Baseline, PAH disease specific concomitant medication, and background PAH medication name. The number of years since PAH diagnosis will be calculated based on the first ralinepag dose date in the APD811-007 study. The summary of PAH history will include descriptive statistics for years since PAH diagnosis and categorical summaries for PAH classification and PAH disease specific concomitant medication at randomization in the parent study.

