10 EFFICACY ANALYSES

10.1 TIME TO CLINICAL WORSENING

Time to the first event of clinical worsening will be calculated and listed. Time to clinical worsening is calculated from the treatment start date in APD811-007 to the first occurrence of clinical worsening. For subjects who do not experience clinical worsening, it will be censored at the last record date of clinical worsening assessment or end of study, whichever is latest.

Summaries and analyses will be performed for time to clinical worsening. Kaplan-Meier estimate will be provided along with the corresponding p-value using log-rank test. In addition, hazard ratio, 95% confidence interval, and p-value will be provided using the Cox proportional hazard model. A Kaplan-Meier plot will also be provided.

10.2 6-MINUTE WALK TEST

The listing of the 6MWT will be organized by treatment group in the parent study, and will include the subject number, visit, assessment date/time (day), last ralinepag dose date/time (day), the last ralinepag dose (micrograms), hours from last ralinepag dose to 6MWT, 6MWD results, and use of supplemental oxygen. The summaries of 6MWD will be provided by treatment group in the parent study for each visit. The summaries will include descriptive statistics for 6MWD and the change from baseline. Baseline is defined as the last 6MWD measured prior to the first dose of ralinepag in the APD811-007 study.

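### Placebo subjects admitted after worsening in APD811-003 are pooled into change-from-baseline with a termination-visit baseline, so rebound or new PAH therapy cannot be separated from a ralinepag effect

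*SAP*

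**What the plan says.** **Who enters.** Protocol 4.2 states: "Subjects who were assigned to placebo in Study APD811-003 and experienced clinical worsening in that study may enroll in Study APD811-007", once end-of-study procedures including RHC are done and the subject's APD811-003 data are locked. Protocol 4.1 describes the population as APD811-003 completers "or who were assigned to placebo and discontinued for clinical worsening and who are deemed appropriate candidates". SAP 3 repeats this.

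**Who is analysed.** SAP 7 bases all analyses, efficacy included, on everyone dosed in APD811-007. SAP 8 presents summaries by parent-study arm and overall. For 6MWD, SAP 10.2 asks for "descriptive statistics for 6MWD and the change from baseline" by visit; 10.3 to 10.5 are similar, with WHO FC shown as a shift. SAP 8.1 allows exploratory subgroups as data permit but names none.

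**Which baseline.** SAP 8.4: "baseline is defined as the last measurement prior to the first dose of ralinepag in the APD811-007 study". SAP 3 identifies the APD811-007 Baseline Visit with the parent study's Termination Visit. Protocol 9.2.2 had made APD811-003 Day 1 the main efficacy baseline and APD811-007 Day 1 the secondary one. SAP 12 declares the change, gives no reason, and keeps no analysis on the earlier baseline.

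**Background therapy.** The SAP 9.3.3 summary covers "PAH disease specific concomitant medication at randomization in the parent study". SAP 9.3.4 adds summaries, by medication name, of drugs ongoing from the parent study and of drugs added in APD811-007.

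**The concern.** A subject who left APD811-003 because of worsening may have a last pre-dose value below his or her usual level. Some return toward that level could occur without ralinepag. Protocol 6.9 also counts the addition or dose change of a PAH drug as a worsening criterion, so an ERA, PDE5-I or sGC stimulator may have been started or increased shortly before entry and still be taking effect afterwards. Either would appear as change from baseline during ralinepag treatment.

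The column matters. The synopsis states that there is no concurrent control. Parent-ralinepag subjects enter already on drug, so parent-placebo is the only arm with a ralinepag-free APD811-007 baseline, and a reader looking for an on-drug change will look there. It is also the only arm that can contain these subjects.

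**Working it through.** The plan gives no figure to reproduce: SAP 6 says that no formal sample size calculation was done, and neither document states how many worsened placebo subjects enrolled. The check is documentary, followed by a scale calculation on stated assumptions.

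**1. Are these subjects separated anywhere?** SAP 7 includes all dosed subjects, SAP 8 splits only by parent arm, and SAP 10.2 to 10.5 add no row, flag or exclusion. They are not separated.

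**2. What is their baseline?** Protocol 7.2.1.2 takes the baseline 6MWT, WHO FC and BNP/NT-proBNP from the final APD811-003 visit. Protocol 4.2 requires RHC among the APD811-003 end-of-study procedures, and protocol Table 2 schedules no further RHC until year 1 or 2. On the scheduled assessments, the SAP baseline is therefore the termination assessment. The APD811-003 Day 1 value, which precedes the worsening, is no longer used.

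**3. Can therapy changes before entry be read from the tables?** In part. SAP 9.3.4 will show a PAH drug begun during APD811-003 and still taken at entry, by name, and the medication listing carries start dates. No table counts subjects who started or increased a PAH drug between APD811-003 randomisation and APD811-007 Day 1, and nothing links such changes to the efficacy results.

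**4. Scale for 6MWD.** Shift in mean change = k × D / n, where k is the number of worsened entrants with a value at the visit, n is the number summarised, and D is the mean change per such entrant that would have occurred without ralinepag.

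All inputs are assumptions: n = 20 parent-placebo subjects; n = 60 overall (the synopsis says approximately 60); usual 6MWD 400 m; a deficit at baseline of 20%, borrowed from one component of the protocol 6.9 definition, so 0.20 × 400 = 80 m. Half recovery gives D = 40 m and full recovery D = 80 m. A continuing decline of 40 m gives D = −40 m.

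| D (m) | n | k = 0 | k = 1 | k = 2 | k = 4 |
|---|---|---|---|---|---|
| +40 | 20 | 0 | +2.0 | +4.0 | +8.0 |
| +80 | 20 | 0 | +4.0 | +8.0 | +16.0 |
| −40 | 20 | 0 | −2.0 | −4.0 | −8.0 |
| +40 | 60 | 0 | +0.7 | +1.3 | +2.7 |
| +80 | 60 | 0 | +1.3 | +2.7 | +5.3 |
| −40 | 60 | 0 | −0.7 | −1.3 | −2.7 |

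If recovery does occur, varying the parent-placebo inputs over n = 15 to 25, usual 6MWD 350 to 400 m, recovery 25% to 100% and k = 1 to 4 gives:

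- lowest: 1 × 0.25 × 0.20 × 350 / 25 = 0.7 m
- highest: 4 × 1 × 0.20 × 400 / 15 = 21.3 m

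SAP 8.2 imputes nothing, so n and k both change from visit to visit and the shift changes with them.

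**The case against.** The case against is substantial, and it rules out several stronger readings.

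- **A reader might infer that the baseline is taken at the worsening event.** Protocol 7.2.1.1 fixes the event time as baseline only for the clinical-worsening endpoint. For the other measures it is the last pre-dose value, which may post-date the event because entry waits for end-of-study procedures and data lock. Therapy already begun may be partly reflected in it.
- **A reader might infer that the value is low by selection and will rebound.** Under protocol 6.9, worsening can be met by hospitalisation or a drug change with no fall in 6MWD. The 20% fall counts only together with worse WHO FC and right heart failure signs, must be confirmed on two tests, and the deterioration must be persistent. That limits regression to the mean. It is also the APD811-007 definition; the one used in APD811-003 is not in the documents. PAH is described as progressive, so these subjects could decline further and pull the mean down.
- **A reader might infer that these subjects lie outside the efficacy objectives.** The completer wording, "Evaluate the effect of ralinepag in subjects with WHO Group 1 PAH who completed Study APD811-003, as determined by the incidence of clinical worsening", belongs to the clinical-worsening objective. The change-from-baseline objective in SAP 2.1 and protocol 2.2 carries no such limit; only the synopsis adds one. Their admission is stated openly.
- **A reader might infer that no summary shows therapy at entry.** SAP 9.3.4 does so by medication name.
- **A reader might infer that the plan credits the change to ralinepag.** The summaries in SAP 10.2 to 10.5 are descriptive and untested, and no text designates the parent-placebo column as the drug effect.

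All of this stands. It does not remove the pooling without separation or the loss of the only planned baseline that preceded the worsening. Being descriptive is also limited protection when, without a control, the raw mean change is the result.

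**Conclusion.** The point holds as a matter of what can be separated, not as a demonstrated bias. In the parent-placebo and overall columns of SAP 10.2 to 10.5, a ralinepag effect cannot be distinguished from rebound after APD811-003 worsening or from PAH therapy started or increased shortly before entry. The parent-ralinepag column is unaffected.

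The documents do not give the size. It is zero if no such subject enrolled. Under the assumptions above, recovery shifts the parent-placebo mean 6MWD change by roughly 1 to 21 m, while continued decline reverses the sign. The high end needs four such subjects among 15 and full recovery of an 80 m deficit. The documents do not support saying that the plan overstates ralinepag's effect; they support saying that its tables cannot show whether it does. This is a modest weakness, worth correcting because the correction is cheap.

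**What to change.** 1. In SAP 10.2 to 10.5, keep the all-dosed parent-placebo and overall rows. Add the same rows excluding subjects admitted after APD811-003 worsening, and list those subjects separately. Replacing the all-dosed rows with completers only is not needed, and would take eligible, treated subjects out of the main display.
2. Add the protocol's APD811-003 Day 1 baseline as a sensitivity analysis for 6MWD, WHO FC and hemodynamics, the variables for which protocol 9.2.2 set it. It should not stand alone: for parent-placebo subjects, change from that point also includes the placebo period, and it does not remove the effect of added therapy.
3. In SAP 9.3.3, add PAH therapy at APD811-007 Day 1, with the number who started or increased a PAH drug since APD811-003 randomisation.

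The cost is SAP wording and a few extra table rows, with no new visits or measurements; the APD811-003 values come from the parent study. The downside is small numbers in the separated group, so a listing may be all that it can support.

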Subjects who require treatment with a prostacyclin/prostacyclin analogue (IV, SC, oral, or inhaled), except for acute vasodilator testing during cardiac catheterization, will be discontinued from the study.

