9.1 ANALYSIS POPULATIONS

Safety Population:

This population will include all subjects who received at least 1 dose of the study drug in this extension study.

Modified Intent-to-treat Population:

The analyses of all efficacy variables will use the Modified Intent-to-Treat Population. This population consists of all subjects randomized who received at least 1 dose of study drug in the extension study, have a baseline measurement, and have at least 1 measurement after entry into the extension study. The Last Observation Carried Forward approach will be used to impute missing values.

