5 INTERIM ANALYSIS

An interim analysis was performed in September 2018 to evaluate the long-term safety and tolerability for all subjects who had received treatment in APD811-007 for at least 1 year. In addition, the objective of the interim analysis was to support proposed Phase 3 studies. Interim analysis was intended to take place in lieu of final study analysis; however, with the discontinuation of Study APD811-007, final analysis is being conducted to serve the protocol objectives with the entirety of study data.

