8.2 PREMATURE DISCONTINUATION AND MISSING DATA

A subject may voluntarily withdraw or be withdrawn from the study by the Investigator at any time for reasons including the following:

- Clinical worsening
- Deviation/noncompliance with the protocol
- A serious or intolerable AE occurs
- The Sponsor or Investigator terminates the study, or
- Withdrawal of consent – any subject may withdraw his/her consent from the study at any time. The Investigator should make a reasonable attempt to document the specific reason why consent is withdrawn.

All available data from all subjects in the Safety Population, as defined in Section 7, will be used as detailed in this analysis plan. Missing data will not be imputed.

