12 CHANGES FROM ANALYSIS PLANNED IN THE PROTOCOL

For the final analysis, the following changes have been made to the analyses that are described in the protocol:

- Safety Population will be used for all summaries (protocol Section 9.1 specifies modified Intent-to-Treat Population for efficacy analyses).
- The protocol separated the primary objective and secondary objectives. The analyses will be based on efficacy and safety, not specifically separating the primary and secondary objectives.
- Protocol Section 6.2 states medical and social history would be updated at Baseline in Study APD811-007. These updates were not collected.
- No imputation will be performed for missing efficacy values (protocol Section 9.1 specifies Last Observation Carried Forward imputation for efficacy missing values).
- Baseline for change from baseline in efficacy values will be the APD811-007 baseline value (protocol Section 9.2 specifies the Day 1 pre-dose measurement in Study APD811-003 as the main baseline, with Day 1 of Study APD811-007 as baseline for a secondary analysis).
- Follow-up vital status (mortality) was not collected.
- Local results of BNP/NT-proBNP are not available.

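### 6MWD will be reported only as observed-case statistics at nominal visits, which overstate the late course of the treated cohort if the subjects who leave walk less than those who stay

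*SAP*

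**What the plan says.** **Missing values.** Protocol 9.1 states for the efficacy variables: "The Last Observation Carried Forward approach will be used to impute missing values". SAP 8.2 says "Missing data will not be imputed". SAP 12 lists the change, "No imputation will be performed for missing efficacy values", and gives no reason for it.

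**Summaries.** SAP 8.4: "Summary analyses will usually be based on the scheduled (nominal) visits with no visit windows applied". SAP 10.2 on the walk test: "The summaries will include descriptive statistics for 6MWD and the change from baseline". These are given by parent-study treatment group and visit; SAP 8 adds an overall presentation for all summary tables. The SAP 8 list of statistics for continuous variables is mean, SD, median, minimum and maximum, without n. No model, sensitivity analysis or target of estimation is given for 6MWD.

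**Confidence intervals.** Protocol 9.2.2 plans estimates with 95% confidence intervals for within-treatment change in 6MWD. SAP 10.2 has none, and SAP 12 does not list their removal.

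**Exit.** Under Protocol 3.1 and 6.13, subjects who need a prostacyclin or analogue, "except for acute vasodilator testing during cardiac catheterization, will be discontinued from the study". That need is also a clinical-worsening criterion (Protocol 6.9). Clinical worsening is a permitted withdrawal reason (Protocol 6.14, SAP 8.2). On premature exit the site tries to carry out the End of Study procedures, which include a 6MWT (Protocol 6.14.1, 7.2.4). No SAP rule assigns that test to a scheduled visit.

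**The concern.** Change in 6MWD is a stated objective in both documents. A mean over whoever attends a given visit answers a different question from the mean over everyone who was treated. The two part company when leaving is linked to walking ability, and the exit rules make such a link plausible. A cohort that declines on average could then show a flatter or even rising curve because of who remains. The walk test most likely to record the decline, the one taken at exit, falls outside the quarterly rows. Since the tables need not show n or an interval, a reader could not see from them how few subjects, or how much uncertainty, lie behind a late value.

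**Working it through.** The plan gives no figure to reproduce. It states no exit rate and no 6MWD standard deviation, so the size can only be bracketed.

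**1. Identity.** Overstatement of the observed-case mean = (share gone) × (mean of stayers − mean of leavers).

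| Share gone | Gap 0 m | Gap 20 m | Gap 50 m |
|---|---|---|---|
| 10% | 0 | 0.10 × 20 = 2 m | 0.10 × 50 = 5 m |
| 30% | 0 | 6 m | 15 m |
| 50% | 0 | 10 m | 25 m |

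The sign depends only on whether leavers walk less than stayers.

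**2. Simulation of year 3.** All inputs are assumptions except the 20% threshold, which is from Protocol 6.9: baseline 400 m, test noise SD 25 m, individual slopes with SD 15, 25 or 35 m/year, unrelated dropout 8% per year, 12 quarterly visits, 200,000 simulated subjects per scenario. Two exit rules were used.
- Harsh: any single test at least 20% (80 m) below baseline leads to exit with probability 0.5 or 1 per quarter.
- Mild: the fall must be confirmed on a second test, and exit then has probability 0.1 per quarter.

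Observed-case mean minus all-subject mean at year 3:

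| Exit rule | True mean change 0 m | True mean change −30 m |
|---|---|---|
| Harsh, slope SD 15 | 5 to 8 m | 11 to 17 m |
| Harsh, slope SD 25 | 19 to 26 m | 30 to 39 m |
| Harsh, slope SD 35 | 39 to 47 m | 52 to 63 m |
| Mild, slope SD 15 | 0.5 m | 1.5 m |
| Mild, slope SD 25 | 4 m | 7 m |
| Mild, slope SD 35 | 10 m | 14 m |
| Unrelated dropout only, slope SD 25 | not run | about 0 m |

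With slope SD 25, a true −30 m reads as about 0 m under the harsh rule at probability 0.5, but as about −23 m under the mild rule.

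**3. Would LOCF have cured it?** A second simulation used 60 subjects, slope SD 5 m per visit, noise SD 25 m, and exit hazard rising from 2% to 15% or 30% per visit once the change falls below −40 m. At visit 12 the observed-case mean was too high by 13 to 36 m. LOCF without the exit test was off by −1 to +17 m, and LOCF including it by −1 to +12 m. With purely random exit and a true decline of 24 m, the observed-case mean was about right, while LOCF was too high by 5 to 6 m.

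**4. Mixed study times.** Ex-ralinepag subjects reach Month 3 at about week 13. Ex-placebo subjects start Treatment Period months after up to 9 weeks of titration, so their Month 3 falls as late as week 13 + 9 = 22. An overall Month 3 row pools the two.

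**5. Precision at about 60 subjects.** If all 60 were followed and their slopes known exactly, the 95% half-width for the three-year mean change would still be 1.96 × 3 × (slope SD) / √60. That is 11 m, 19 m and 27 m for slope SDs of 15, 25 and 35 m/year. Noise and dropout widen it.

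**The case against.** - **Exit is looser than the harsh rule assumes.** In Protocol 6.9 the 20% fall is one part of a three-part criterion: confirmed on two tests, with functional class worsening and with right heart failure unresponsive to diuretics. Protocol 3.1 lets the investigator keep a worsened subject on treatment. Sponsor closure (SAP 3) is an exit unrelated to walk distance. This stands; it is why the direction is conditional and the range must include values near zero.
- **Attrition is reported elsewhere.** SAP 9.1 tabulates discontinuation reasons and treatment completion by visit, SAP 10.1 analyses time to clinical worsening, and SAP 11.2 summarises deaths. True, but these show that subjects left; they do not adjust the 6MWD summaries.
- **The observed-case mean is accurate for attenders.** It is. The SAP does not say that attenders are the population meant.
- **Visit windows are already tight.** Protocol 6.15 allows ±5 days for quarterly visits, so analysis windows matter mainly for exit tests and for the titration offset. The offset affects the overall column, not the parent-group columns.
- **A model has its own target.** It estimates the distance had subjects remained in the study, which is hypothetical for those who died or moved to a prostacyclin. This stands and should be stated in the SAP.

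A reader might also infer that interim results prompted the loss of LOCF, since the SAP reports that "An interim analysis was performed in September 2018" and cites a protocol amendment of May 2019. The documents openly declare the change and do not say when or why it was decided, so they do not support that inference.

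**Conclusion.** The plan leaves a selected description as its only 6MWD analysis, with no rule for exit tests and no confidence interval. Late means overstate the course of all treated subjects if leavers walk less than stayers. The exit rules make that plausible, but the documents do not establish it. Under the assumptions above the year-3 overstatement runs from about 1 m to over 60 m; it is near zero if exits are unrelated to 6MWD.

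Three stronger readings should be resisted. The late curve is not shown to be biased upward as a matter of fact. Dropping LOCF is not itself the error, because LOCF can also be biased. The argument does not carry over to hemodynamics, where the protocol schedules catheterization once, at 1 or 2 years or at approval of Amendment 2 (with one at early exit if none in the previous year), and SAP 8.4 foresees a baseline and post-baseline summary.

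The undisclosed loss of the 95% confidence intervals is a plain discrepancy between protocol and SAP and rests on no assumption. No formal test of 6MWD is affected, so this is a cheap improvement to a descriptive endpoint.

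**What to change.** Keep the observed-case tables, add n at each visit, and label them as describing subjects still attending. Add to SAP 10.2:

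1. A likelihood-based repeated-measures model (MMRM or random slope) using every recorded 6MWT, reporting change from baseline with 95% CI. State that it assumes dropout depends on recorded values and that it targets the distance had subjects remained in the study.
2. Study-day windows counted from the first APD811-007 dose in both groups, with early-termination and End of Study tests assigned to them.

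The model's intervals restore those planned in Protocol 9.2.2 for 6MWD; if they are not to be reported, SAP 12 should say so and why. SAP 12 should also give the reason for dropping LOCF. A last-observed-value line for 6MWD is optional. Do not add one for BNP/NT-proBNP: SAP 12 says local results are unavailable, so early central values would be carried forward for long periods.

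Cost: SAP wording, one model and a windowing step, with no new data. The price is reliance on a missing-at-random assumption that cannot be checked, wide intervals at about 60 subjects, and a late curve that may look less favourable.
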